After informed consent, each subject will undergo a complete physical examination by a physiatrist board certified in SCI medicine ([name] or [name] or [name]), including neurologic assessment and American Spinal Injury Impairment Scale Classification (AIS) examination. Participants will be evaluated every 3 months after treatment initiation and then annually to assess any adverse effects and to check compliance. Testosterone measurements will be acquired every 4 weeks during the intervention to determine the serum level and the dose will be adjusted to allow ~30% increase from baseline ([name]). A prostatic abnormality on digital rectal examination will also lead to exclusion. An increase in serum or plasma prostate specific antigen (PSA) of 1.4 ng/ml above baseline will result in immediate cessation of TRT.

Measurements. All participants will undergo body composition assessments (**specific aim 1**), metabolic studies (**specific aim 2**) and muscle biopsies (**specific aim 3**). All testing procedures will be conducted one week prior to training (**baseline**), 6 months following training (**mid-intervention**) and one week after the end of 1 year of training (**post-intervention**). At each time point, measurements will include estimation of body composition, anthropometry, and dual x-ray absorptiometry (DXA). MRI scans will be obtained for thigh skeletal muscles to determine IMF and CSA.¹⁴⁻¹⁸ Participants will remain at the VA Medical Center for dinner, and overnight. After an overnight fast the subject will be gently awakened at 6 AM to measure BMR. At 6.30 AM an IV line will be placed and blood will be drawn for serum total T and IGF-1 concentrations at 6.30, 7.00 and 7.30 AM. Resting blood pressure and fasting metabolic markers will be obtained

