LPWS or Standard NMES. Training will be conducted twice weekly using a S88X dual output square pulse Grass Stimulator (for research use only) and the current will be set as shown in Table 3.^{22,25} According to the Food and Drug Administration (FDA), all functional non-invasive electrical stimulators are considered a non-significant risk device and do not necessarily need IDE application and only require IRB approval prior to the trial. Long pulse duration (120-150 ms) is used to offset the low resting membrane potential of the denervated muscles.²²⁻²⁵ When tetanic contraction is achieved, the pulse duration will be shortened gradually by 5-10 ms/ month to reduce the likelihood of skin irritation (**Table 3**). We will explore the best stimulation parameters necessary to evoke twitches/ tetanic contraction of the knee extensor as far as the frequency and amplitude of the current for each participant. Initially, we will set the pulse duration at 150 ms, frequency at 2 Hz and the amplitude of the current will be gradually increased from 0 mA by 10 mA intervals up to 200 mA. The current (mA) and the pulse duration (ms) that causes full knee extension will be recorded for each session. An example progression of the stimulation parameters is listed in table 3. Based on previous work, some participants may take up to 6 months to lift their legs against gravity.^{24, 62} Therefore, a one year intervention may be a reasonable duration to load the muscle and evoke hypertrophy especially after years

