of denervation. For the TRT+ standard NMES (control group), a Theratouch 4.7 stimulator (0-200 mA) or battery operated stimulator (0-100 mA) that elicits direct current, a 5 second/5 second work/rest ratio will be used with a 3-minute rest between sets, 30 Hz, 450µs pulses.52-55 For the control group over a 1-year period, participants will have the option to perform a home based training using our established videoconference telehealth system to monitor their training using a hand-held battery operated stimulator (see supplement). Study visits will be limited to once a month throughout the 1-year period to refill their 30 days stock of TRT patches. Training sessions will consist of 4 sets of 10 repetitions of LPWS NMES-induced knee extensions and will last for 30-40 minutes. All training procedures will be conducted with the participants sitting in their wheelchairs with enough space to clear their foot off the ground. 52-55 Two large 8 X10 cm² (Uni-Patch, Wabasha, MI, USA) adhesive carbon electrodes will be placed on the skin over the knee extensor muscle group.⁵²⁻⁵⁵ Once the participant completes 40 repetitions of knee extension, ankle weights will be increased gradually by 2 lbs. per week (not to exceed 30 lbs.). In our prior work the maximum weight was below 30 lbs. because of concerns over the possibility of causing condylar fractures. For the control group (TRT+ standard NMES), the direct current at 450 µs will be turned up to 200 mA for 10 times/set; which is unlikely to cause either twitches or tetanic contraction of the stimulated muscle. Table 3 Example of progression of the stimulation parameters over 1 year 24

10	Table 3. Example of progression of the sumulation parameters over 1 year								
	Months of	Pulse Width	Inter-Pulse	Frequency	Amplitude of	Weights			
	Training	(ms)	interval	(Hz)	current (mA)	(lbs.)			
	-		(ms)						
	1-3	120-150	400	2	up to 200	0			
	4-6	90-120	400	15-25	up to 200	0			
	6-9	60-90	100-400	25-30	up to 200	2 lbs./ 40			
						reps/session			
	9-12	30-60	10-12	25-30	up to 200	2 lbs./ 40			
					-	reps/session			

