Testosterone replacement Therapy (TRT). Testosterone will be administered via transdermal patches (Androderm Corp., Palo Alto, CA) that will deliver between 4-8 mg/day.³⁹ The Endocrine Society guidelines recommend one or two patches of 5 mg/day. Because Transdermal Androderm patches are either 2 or 4 mg we will proceed with 4-8 mg/day. Two patches that deliver 4-8 mg/day initially will be worn at all times except when bathing. Participants will be instructed to change patches once a day before bedtime. Patches will be worn daily on a dry skin over the right or the left shoulder, abdomen or thighs and the application sites will be rotated to avoid skin irritation for 1 year.⁶⁷ TRT will be administered for 1 year because it has the maximum effects on lean mass after SCI. The dose will be decreased to 2 mg/day if the serum T concentration is more than 1000 ng/dL (34.7 nmol/L) and the participant will be reeducated in the patch technique if the concentration is less than 250 ng/dL (8.7nmol/L) above the pretreatment concentration. Serum prostate-specific antigen (PSA) level will be measured to ensure normal concentration according the guidelines provided by the Endocrine Society. Patch compliance will be monitored by inventory of the number of returned patches each month.⁷⁸ Free T will be calculated using total T, sex hormone binding globulin (SHBG) and albumin equation.79

Specific aim 1. We will compare the effects of TRT+LPWS compared to TRT+ standard NMES (control group) on the size of thigh skeletal muscle, intramuscular fat (IMF) and leg lean mass. Both groups will receive TRT for 1 year. Anthropometrics, DXA and MRI will be performed at baseline, 6 and 12 months post-interventions to measure thigh skeletal muscle size, IMF and leg lean mass.

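### Minor: two example rows of Table 3 pair pulses with frequencies that cannot be delivered, and a 30% testosterone rise always falls under the 250 ng/dL re-education trigger

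*Combined protocol and SAP*

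**What the plan says.** **Stimulation** (section 4, LPWS or Standard NMES). The paragraph says that "the current will be set as shown in Table 3". It later adds: "An example progression of the stimulation parameters is listed in table 3". The table caption repeats the example label. The starting point is explicit: "Initially, we will set the pulse duration at 150 ms, frequency at 2 Hz", with current raised in 10 mA steps to 200 mA. Frequency and amplitude are then explored for each participant. Once a tetanic contraction is obtained, the pulse is to be shortened by 5-10 ms a month.

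Table 3 lists pulse width (ms), inter-pulse interval (ms) and frequency (Hz). The months 4-6 row reads "90-120 400 15-25" and the months 6-9 row reads "60-90 100-400 25-30". On what is written down at each visit: "The current (mA) and the pulse duration (ms) that causes full knee extension will be recorded for each session".

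**Testosterone** (section 4). Serum testosterone is measured every 4 weeks, and "the dose will be adjusted to allow ~30% increase from baseline". Under Testosterone replacement Therapy, the participant is re-educated in patch technique "if the concentration is less than 250 ng/dL (8.7nmol/L) above the pretreatment concentration", and the dose is cut to 2 mg/day above 1000 ng/dL. Men with a baseline above 800 ng/dL are excluded (section 4, Exclusion; section 5, item I.e).

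**The concern.** Width, gap and frequency are not independent: any two fix the third. In the middle two rows of Table 3 they disagree by a wide margin. For months 4-9 a reader is left with two descriptions of the active stimulation, roughly 2-6 Hz from width and gap or 15-30 Hz as stated. Frequency is one of the parameters the plan itself names for obtaining a twitch or tetanic contraction. The session record, as described, holds current and pulse duration, so it would not later show which frequency was used.

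On testosterone, one rule aims for a rise that another rule treats as too small. A man exactly where titration wants him would be handled as if his patches were being misapplied.

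**Working it through.** **Stimulation.** Inputs are the three columns of Table 3. If frequency means pulses per second, then frequency = 1000 / (width + gap), both in ms.

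The plan's own starting row checks the formula. At 150 + 400 = 550 ms the rate is 1.82 Hz, and at 120 + 400 = 520 ms it is 1.92 Hz. Both agree with the stated 2 Hz after rounding.

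| Months | Width + gap (ms) | Implied Hz | Ceiling with zero gap (1000/width) | Stated Hz |
|---|---|---|---|---|
| 1-3 | 520-550 | 1.8-1.9 | 6.7-8.3 | 2 |
| 4-6 | 490-520 | 1.9-2.0 | 8.3-11.1 | 15-25 |
| 6-9 | 160-490 | 2.0-6.3 | 11.1-16.7 | 25-30 |
| 9-12 | 40-72 | 13.9-25.0 | 16.7-33.3 | 25-30 |

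- Months 4-6: one cycle at 15-25 Hz lasts 1000/15 = 66.7 ms down to 1000/25 = 40 ms. The pulse alone is 90-120 ms.
- Months 6-9: one cycle at 25-30 Hz lasts 40 ms down to 33.3 ms. The pulse alone is 60-90 ms.
- Reading the interval as onset-to-onset does not help: 1000/400 = 2.5 Hz in months 4-6, and 2.5 to 1000/100 = 10 Hz in months 6-9.
- Months 9-12 fit at one corner only: 30 + 10 = 40 ms, which is 25 Hz. At 30 Hz a 10 ms gap leaves 33.3 - 10 = 23.3 ms, below the listed minimum width of 30 ms.

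Which column is wrong? Apply the shortening rule at its faster rate, 10 ms a month, from 150 ms at the outset: 120 ms at month 3, 90 at month 6, 60 at month 9 and 30 at month 12. Those are the edges of the width column. The widths therefore agree with the text, which points to the frequency column.

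**Testosterone.** Inputs are a target rise of 30%, a re-education trigger of 250 ng/dL, a maximum eligible baseline of 800 ng/dL and a dose cut above 1000 ng/dL.

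- Unit check: the plan equates 1000 ng/dL with 34.7 nmol/L, so 250 ng/dL is 0.25 × 34.7 = 8.7 nmol/L, as printed. The 250 is not a conversion slip.
- Largest on-target rise: 0.30 × 800 = 240 ng/dL, below 250. The two rules would meet only at a baseline of 250/0.30 = 833 ng/dL, which is excluded.
- Rise needed to avoid the flag: 250/300 = 83%, 250/400 = 62.5%, 250/600 = 42% and 250/800 = 31%, at baselines of 300, 400, 600 and 800 ng/dL.
- Target against cap: 1000/1.30 = 769, so above a baseline of about 769 ng/dL the 30% target is itself over the dose-cut level.
- Trigger against cap: 1000 - 250 = 750, so above a baseline of 750 ng/dL no level avoids both the flag and the cut.
- Loosening the target to 35% (an assumption about how far the approximation stretches): the flag is avoided from 250/0.35 = 714 ng/dL and the cut up to 1000/1.35 = 741 ng/dL. Only baselines of 714-741 escape both.
- Illustration from the preliminary trial's NMES+TRT group, mean baseline 413 ng/dL: the target is 1.30 × 413 = 537 and the re-education line is 413 + 250 = 663. The mean reached was 525, a rise of 112 (27%). Those men used 2-6 mg/day and this trial uses 4-8 mg/day, so rises may be larger here.

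**The case against.** A reader might infer that Table 3 fixes the active arm's settings, so that the trial's intervention cannot be delivered as designed. The documents do not support that. The table is labelled an example twice. The sentence sending the reader to it speaks of the current, a word the plan also uses for amplitude in mA, and the amplitude column (up to 200 mA in every row) has no such problem. The text gives a clear start of 150 ms and 2 Hz, progression follows the participant's response, and frequency is left to individual exploration. Staff cannot deliver an impossible pair and would have to settle on a workable one. All of this stands, and it reduces the matter to a wrong example and an incomplete record. It does not make the two rows right.

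A reader might also infer that the testosterone rules create a safety problem or favour one arm. Neither follows. Re-education changes no dose, removes nobody and does not enter the analysis. Both arms follow the same rules, and adherence is tracked separately by counting returned patches. Nor will every man in practice be flagged: the result holds at exactly 30%, the target is approximate, and men who overshoot it by enough will clear 250 ng/dL. What stands is that the two rules disagree by a wide margin at ordinary baselines, where the approximation cannot close the gap.

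**Conclusion.** Both items are wrong as written and minor. If Hz means pulses per second, the months 4-6 and 6-9 rows are impossible under any reading of the interval. The stated frequency is 7.3 to 13 times what width plus gap allow in months 4-6 (15/2.04 to 25/1.92), and 4.0 to 14.7 times in months 6-9 (25/6.25 to 30/2.04). The months 9-12 row works at a single combination. If frequency means something else, such as a burst rate, the plan does not say so. That the frequency column is the one in error is an inference from the match between the widths and the 10 ms/month rule; at 5 ms/month, or with shortening delayed until a tetanic contraction appears, the match would not be exact.

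At a 30% rise the re-education trigger is met at every eligible baseline, and above about 769 ng/dL the target also breaches the dose-cut level. The consequence is unneeded re-education in both arms, and a conflict between target and cap only at the highest baselines. No effect on the primary comparison, the power or the analysis is shown for either item.

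**What to change.** 1. Keep the listed widths and gaps and restate frequency as 1000/(width + gap): about 2, 2, 2-6 and 14-25 Hz for the four periods. The sponsor's clinicians should confirm that these rates are what they intend.
2. If 15-30 Hz is really wanted in months 4-9, width plus gap must total 40-66.7 ms in months 4-6 and 33.3-40 ms in months 6-9. The widths, the gaps and the 5-10 ms/month rule would then all have to change: even 10 ms a month from 150 ms leaves 90 ms at month 6. If frequency has another meaning, define it.
3. Add delivered frequency and inter-pulse interval to the session record.
4. Tie the re-education trigger to the titration target, for example a rise clearly below 30% of baseline, and state that the 1000 ng/dL cap overrides the target. The clinicians should choose the values.

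Taking item 1 rather than item 2, the cost is one corrected column, a sentence or two on testosterone and two fields on a form, with no extra participants or procedures. Item 2 is a larger rewrite of the stimulation schedule.

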-8 mg/d) will be re-placed daily on alternating skin sites at bedtime for 1 year. Randomization will be done at the end of the two-day assessment period using a random number generator computer program (baseline). Participants will be block randomized based on the degree of denervation (lower or higher than 50% of compound muscle action potential (CMAP) of the standard normal femoral nerve values). Both groups (TRT+LPWS & TRT+ standard NMES) will undergo 1 year of supervised unilateral progressive RT, twice weekly, using ankle weights. The two-day assessment period will be repeated using the same sequence at 6 months and after 1 year. Prior to training, we will perform multiple neurophysiological tests to confirm LMN denervation of the knee extensor muscle group. The first technique is to place the surface NMES electrodes on knee extensor muscle group and increase the current (30 Hz, 450 µs) gradually up to 200 mA. If the knee extensors show visible elicited contraction, then the participant will be disgualified from the study. If there is no response, participant will then be escorted to the EMG lab and further testing for evidence documenting muscle denervation will be performed by a trained electromyographer. Briefly, participants will undergo a femoral nerve motor conduction study with recording of the CMAP from the vastus medialis (VM) with supramaximal femoral nerve stimulation just below the inguinal ligament. The participant will undergo needle EMG of the vastus medialis to determine the presence and intensity of spontaneous muscle fiber fibrillation potentials to quantify the level of denervation. A monopolar EMG needle electrode will be inserted into the VM muscle to record spontaneous intramuscular activity in the resting muscle.

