Statistical Analyses. Means and standard deviations or frequencies and percentages will be reported for all data. Similar summaries will be provided for all outcome and biomarker data separately at baseline, 6-, and 12-months. A repeated-measures ANOVA will be used to analyze the primary study outcome, skeletal muscle size, with treatment, time, and the interaction of these variables included in the model. A first order autoregressive correlation structure will be used to capture the dependency within subjects' outcomes. A specific contrast will be used to determine if the change from baseline for the treatment group is different than that of the control group. A model selection procedure will be performed due to the relatively large number of predictor variables compared to the number of subjects for specific aims 2 and 3. A penalized random effect model will be used to suggest the important predictors for each outcome separately. These include each specific predictor mentioned in the specific aims as well as injury characteristics.⁸⁴ A parsimonious model will be chosen by the Bayesian information criterion. Since the aforementioned model is well-suited for model selection, but results in biased parameter estimates, an unpenalized random effects model will be fitted based on the parsimonious model and used for inference. Study period will be included in all analyses, and a time by group interaction will be included for the analyses associated with Specific Aim 3. All statistics will performed with R (3.3.0) with the 'glmmLasso' package. Prior to any statistical analysis, any of the biomarkers may be transformed to ensure all statistical assumptions are met. A simulation study was used to determine the power achieved from the proposed study if 5% of subjects were assumed to drop out at the 12-month observation point. One thousand datasets were created with Cohen's d varying between 0.5 and 2.0, with the anticipated 24 subjects being equally allocated to the treatment and control groups and the subjects' outcomes having a correlation of 0.25. A linear mixed-effects model was used to analyze the simulated data using a one-sided test at α =0.05. Results of the study show that this design will have the power to detect differences of d=1.28 with 80% power and d=1.48 with 90% power. An intent-totreat approach will be used to deal with missing data. If the missing data is due to drop-out, the statistical methods are valid as long as the data mechanism is considered missing at random or missing completely at random.

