The Hunter Holmes McGuire VAMC and the surrounding 13 spokes will be notified of the clinical trial once it is approved for imitation. Despite the large Spinal Cord Dysfunction (SCD) registry (n=1,800), SCI persons with LMN denervation represent a small subgroup of the entire population and recruitment may be challenging. The primary focus will be to include Veterans with SCI and the Civilians with SCI will be only considered in case we fall short to complete our target sample size. The inclusion of Civilians with SCI will allow generalizing the findings of the current trial to the entire SCI population.

c. Rationale for conducting the trial up to 1 year

In the current trial, we will include SCI persons with different levels of denervation. It is clear that skeletal muscles with denervation atrophy may take 3-6 months to evoke a strong tetanic contraction that is capable of moving the leg against gravity. Our data showed that loading the muscle is the best approach to evoke muscle hypertrophy and therefore, adding another 6 months may be a reasonable period to load the muscles. Besides the duration of the intervention has also considered the frequency (twice weekly) and not to overly stress the muscle to cause exercise induced muscle damage. Regarding applications of TRT, it is clear that using transdermal TRT patches may also need up to 1 year to induce a modest effect on lean mass.

d. Inclusion of women and minorities: Women will not be included in the current study

because administering TRT is neither appropriate nor safe. Department of Veteran Affairs has limited access to Veteran women with motor complete SCI. They are also at risk of virilizing actions of testosterone, therefore, we were planning to limit this trial only to men with SCI. No vulnerable populations will be included and persons under 18 will be excluded.

e. Exclusion: Every effort will be made to ensure each subject's safety or to exclude participants with current medical conditions that may confound the results. A conditional exclusion is those who will fail to tolerate the LPWS paradigm will also be excluded. Pain tolerance will be examined by gradually increasing the current in 10 mA intervals starting from 0 mA. If pain arises before a visible contraction, the subject will be automatically excluded from the trial.

The list of exclusion criteria will include the followings

- 1. Diagnosis of neurological injury other than SCI;

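### The primary test compares raw changes and does not adjust for baseline muscle size; at the plan's own correlation of 0.25 this raises the variance by about 52%

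*Combined protocol and SAP*

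**What the plan says.** Section 4, Statistical Analyses, plans a repeated-measures ANOVA of skeletal muscle size "with treatment, time, and the interaction of these variables included in the model". For the covariance it states: "A first order autoregressive correlation structure will be used to capture the dependency within subjects' outcomes". The primary contrast is there to "determine if the change from baseline for the treatment group is different than that of the control group"; the visit is not named. Muscle size is measured at baseline, 6 and 12 months.

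The power simulation in the same paragraph has 24 men in two equal arms, 5% dropout at 12 months, a one-sided test at 0.05, and the subjects' "outcomes having a correlation of 0.25". It reports 80% power at d=1.28 and 90% at d=1.48.

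On allocation, section 4 says: "Participants will be block randomized based on the degree of denervation". The cut is at 50% of the normal femoral CMAP. That stratum is not in the primary model. The covariate selection described in Statistical Analyses is for Aims 2 and 3 only.

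**The concern.** Baseline muscle size enters the primary model as one of the repeated outcomes. It is not a covariate, and the free treatment term lets the two arms have different baseline means. With complete data the contrast is therefore the plain difference between arms in mean change. Subtracting the whole baseline value is efficient only when baseline and follow-up are very highly correlated. At a low correlation it adds baseline noise to the comparison.

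Precision is scarce with 24 men, and the protocol itself expects recruitment to be difficult. Baseline muscle size is measured in every man before randomisation, so the information is already paid for.

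**Working it through.** **Inputs (section 4, Statistical Analyses).** 12 men per arm, N=24; one-sided α=0.05; d=1.28 and 1.48 in outcome-SD units; correlation ρ=0.25; 5% dropout at 12 months. Equal SDs at baseline and 12 months are assumed, as a single Cohen's d implies. The contrast is taken at 12 months.

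**Reproducing the stated power.** With constant correlation, the variance of a change is 2(1−0.25)=1.500. The standard error of the difference is √(2×1.500/12)=0.50, so the noncentrality at d=1.28 is 1.28/0.50=2.56. The noncentral t gives 79.8% power at d=1.28 and 88.9% at d=1.48, without dropout. A simulated mixed model with constant correlation and 5% dropout (2,000 trials) gives 78.7% and 88.4% with a t reference, or 79.8% and 89.3% with a normal reference. The plan's 80% and 90% are reproduced.

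Other readings do not fit (normal approximation, 12 per arm, at d=1.28 and 1.48):
- two-sided test: 73% and 84%
- 12-month value alone: 93% and 98%
- mean of the two changes: 91% and 96%
- ANCOVA: 94% and 98%
- 0.25 as the adjacent-visit value of an AR(1): 74% and 84%

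The stated power therefore rests on the unadjusted 12-month change with a baseline-to-12-month correlation of 0.25.

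**Comparison with baseline adjustment.** In outcome-variance units:
- change: 2(1−ρ)
- ANCOVA: (1−ρ²)×(1+1/(N−4)) = (1−ρ²)×1.05, where 1.05 is the price of estimating the slope
- ratio: [2/(1+ρ)]/1.05

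At ρ=0.25 this is 1.500 against 0.9375×1.05=0.984, a ratio of 1.524.

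| ρ | Change | ANCOVA | Ratio | Power at d=1.28, change / ANCOVA |
|---|---|---|---|---|
| 0.25 | 1.500 | 0.984 | 1.52 | 80% / 92% |
| 0.5 | 1.000 | 0.788 | 1.27 | 92% / 96% |
| 0.8 | 0.400 | 0.378 | 1.06 | 99.9% / 99.9% |
| 0.9 | 0.200 | 0.1995 | 1.00 | – |
| 0.95 | 0.100 | 0.102 | 0.98 | – |

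Power is one-sided, without dropout. Break-even is at ρ=2/1.05−1=0.905. The large-sample ratio, without the 1.05, would be 1.60 at ρ=0.25.

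At ρ=0.25 the d detectable with 80% power falls from 1.28 to 1.28×√(0.984/1.500)=1.04. The unadjusted test would need about 24×1.524≈37 men to match.

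**Simulation.** Without dropout, 40,000 trials give 80% and 92%, with variance ratios of 1.52 to 1.54. With 5% dropout, power is 78% against 90% at d=1.28 and 87% against 96% at d=1.48. Under the null both tests reject in about 4.9% of trials.

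**Stratum.** With complete data and saturated treatment-by-time means, adding the CMAP stratum as a main effect to the planned model leaves the 12-month change contrast and its variance unchanged. Added to ANCOVA, a stratum with no prognostic value (6:6 or 2:10 split) changed power by no more than about 0.1 percentage point.

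**The case against.** The planned contrast is valid, and the sample size was calculated for it, so one could call adjustment a preference between two sound methods. The 52% depends on one planning value. Section 5 says that "we will include SCI persons with different levels of denervation"; stable differences between men would push the correlation up and shrink the gain. This stands: the point concerns efficiency and its size is conditional. Section 3 also reports widely varying response to stimulation training, which would push the correlation down.

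The formula also needs equal SDs, while the plan expects growth of 25% or more. Taking a follow-up SD 1.25 times baseline as an illustration, the ratio at ρ=0.25 is 1.36 if only the treated arm spreads and 1.26 if both do. In the latter case it is 1.07 at 0.5 and 0.97 at 0.7, so break-even falls below 0.7. The benefit is smaller but does not reverse into a material loss: the ratio cannot fall below 1/1.05≈0.95.

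Finally, the table assumes a correct standard error, whereas the plan prescribes AR(1). If the true correlation is constant across visits, the AR(1) standard error is about 10% too large at ρ=0.25 (type I error 3.4% to 4%, power about 75% at d=1.28) and about 32% too large at 0.8 (type I error about 1.5%). The small loss shown at 0.8 therefore applies to a change test with a correct standard error. This makes the planned test more conservative still and does not favour keeping it.

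**Conclusion.** The concern holds as a loss of precision, not of validity. The excess variance is about 52% at the plan's correlation of 0.25, and the power gain at d=1.28 is about 12 percentage points with or without the 5% dropout. The loss is about 6% at ρ=0.8 and nil near 0.9. These figures assume a 12-month contrast, equal SDs at the two visits and constant correlation. If 0.25 were instead the adjacent-visit AR(1) value, the baseline-to-12-month correlation would be 0.25²=0.0625 and the ratio 1.79; the reading used here gives the smaller loss. With the true correlation unknown, the balance is lopsided: a possible gain of about half the variance against a cost of at most about 5%. The omitted stratum is secondary, and its gain cannot be quantified from the documents.

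**What to change.** Replace the raw-change contrast in Statistical Analyses with a pre-specified baseline-adjusted comparison. Either of these would do:

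- ANCOVA or MMRM on the 6- and 12-month values, with baseline muscle cross-sectional area as covariate.
- A longitudinal model of all three visits with a common baseline mean. This also retains men who drop out before 12 months.

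Name the adjusted 12-month difference as the primary estimate. Do not rely on AR(1); an unstructured covariance avoids the misfit described above. Include the CMAP stratum in the adjusted model so that the analysis reflects the randomisation. Adding it as a main effect to the present model would change nothing.

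The cost is a change of wording before unblinded analysis and one or two degrees of freedom. No extra measurements or participants are needed.
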